1.0 Study Summary

Study Title	Feasibility, acceptability, and preliminary efficacy of combined transcranial direct current stimulation and mindfulness for pain after total knee arthroplasty
Study Design	Pilot randomized controlled trial
Primary Objective	Assess feasibility/acceptability of the intervention
Secondary Objective(s)	Assess preliminary effectiveness on pain intensity and pain interference with activities
Research Intervention(s)/Investigational Agent(s)	Combined Mindfulness-based intervention (MBI) + transcranial direct current stimulation (tDCS) vs sham MBI+sham tDCS
IND/IDE #	
Study Population	Preoperative patients undergoing total knee replacement (TKR)
Sample Size	40
Study Duration for individual participants	1 month
Study Specific Abbreviations/Definitions	CSPS: chronic post-surgical pain MBI: mindfulness-based intervention tDCS: transcranial direct current stimulation EG: experimental group CG: control group

2.0 Objectives*

2.1 The goal of this project is to assess the preliminary feasibility, acceptability, and efficacy of self-administered preoperative tDCS+MBI in older adults (50+) undergoing TKR. The central hypothesis is that combined preoperative tDCS+MBI will decrease postoperative analgesic consumption, postoperative clinical pain severity, as well as preoperative pain-related cortical response. We will accomplish three aims using a randomized controlled trial.

2.2 *Hypotheses:*

To determine the effects of 5, 20-minute preoperative self-administered tDCS sessions combined with brief MBI on analgesic medication consumption following TKR

Hypothesis 1: participants receiving preoperative active tDCS+MBI will show reduced postoperative analgesic consumption.

To determine the effects of 5, 20-minute preoperative self-administered tDCS sessions combined with brief MBI on postoperative pain severity following TKR

Hypothesis 2: participants receiving preoperative active tDCS+MBI will show reduced postoperative pain intensity and pain interference with physical and emotional function 5 days and 1 month after TKR.

To explore the effects of 5, 20-minute preoperative self-administered tDCS sessions combined with brief MBI on preoperative endogenous pain modulation

PROTOCOL TITLE:

Hypothesis 3: participants receiving preoperative active tDCS+MBI will show improved preoperative endogenous pain modulation.

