4.0 Study Endpoints*

- 4.1 Measures will be taken by a research assistant via a telephone interview using a Qualtrics® survey. Outcome measures will be taken at 4 time points: 1) baseline (before preoperative active/sham tDCS+MBI), 2) after 5 sessions of preoperative active/sham tDCS+MBI, 3) after surgery, and 4) 1 month after surgery (see table below)
- 4.2 Primary endpoint: Analgesic consumption. The dose of every opioid received within 5 days postoperatively will be transcribed and converted into standardized parenteral morphine equivalents using the Centers for Disease and Control Prevention Guidelines on opioids⁴². A total in milligrams will be calculated for each day and means will be obtained for all groups.
- 4.3 Secondary endpoints: pain severity (numeric rating scale 0-100), pain interference with activities (numeric rating scale 0-10), depression and anxiety (PHQ-4), pain catastrophizing (Pain Catastrophizing Scale), multimodal quantitative sensory testing (QST) including heat pain (e.g., threshold, tolerance), pressure pain threshold, punctate mechanical pain (e.g., suprathreshold ratings and temporal summation), and Conditioned Pain Modulation (CPM), acceptability and feasibility

Day/month	B	Preoperative phase	Postoperative phase
-----------	---	--------------------	---------------------

PROTOCOL TITLE:

		Day 1	Day 2	Day 3	Day 4	Day 5	Day 1	Day 2	Day 3	Month 1
Medical History Questionnaire	X									
Analgesic consumption (primary outcome)							X	X	X	X
Clinical Pain severity (secondary outcome)										
NRS	X					X			X	X
BPI	X					X			X	X
PHQ-4	X					X			X	X
PCS	X					X			X	X
Pain-related Cortical Response (secondary outcome)										
QST measures	X					X				
Acceptability and feasibility										
tDCS + MBI experience questionnaire						X				
Side effects questionnaire		X	X	X	X	X				

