Analgesic consumption. The dose of every opioid received within 5 days postoperatively will be transcribed and converted into standardized parenteral morphine equivalents using the Centers for Disease and Control Prevention Guidelines on opioids ⁴². A total in milligrams will be calculated for each day and means will be obtained for all groups.

Pain severity. Pain intensity is a global indicator of the pain experience. It will be assessed with a numerical rating scale (NRS) (0-100) with the anchors being no pain at all (0) and worst possible pain (100). This type of scale is recognized for its reliability, validity and sensitivity in various clienteles and settings ^{41,43,44} and is a reliable and well-validated measure with good ability to detect pain change in adults with knee OA ⁴⁵. Four different measures of pain intensity will be taken: 1) average pain upon movement in the past 7 days, 2) worst pain upon movement in the past 7 days, 3) present pain upon movement, and 4) present pain at rest. As suggested by the IMMPACT group in regard to pain core domains in clinical trials ^{41,46}, the impact of pain on various aspects of daily living will be assessed with interference items of the Brief Pain Inventory (BPI) ⁴⁷. The BPI has been successfully validated patients suffering from OA and undergoing TKR ^{6,48}. It includes seven items and evaluates the impact of pain on general activity, mood, walking, work, relationships, sleep, and enjoyment of life via a NRS (0-10). Each item represents a subscale and can be scored and analyzed individually (0-10), with the anchors being “does not interfere” (0) and “completely interferes” (10). A total interference score can also be calculated by taking the sum of all the items. Additionally,

PROTOCOL TITLE:

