For Aim 1, analgesic consumption measured on 3 consecutive days will be summarized into one number for each subject. Two-sample t-test (or non-parametric alternative) will be employed to determine the significance of the difference between the active and the sham tDCS+MBI groups. Multivariate linear regression will be further employed to account for potential confounding factors, including selected baseline demographics and clinical characteristics (e.g., age, sex, race, and body mass index). For Aim 2, we will conduct multivariable regression analysis to compare the change in clinical pain intensity (NRS, BPI, PHQ-4, PCS) from baseline to Day 3 in the postoperative phase after controlling for baseline and other confounding factors (e.g., age, race, sex, baseline NRS, consumption of pain medications). We will also determine whether the improvement conferred by active tDCS+MBI can be sustained by comparing the clinical pain intensity changes from baseline to 1 month between the active and the sham groups. We will also conduct sex-stratified analysis and explore whether there exists sex difference in these effects. For Aim 3, the QST dataset for endogenous pain modulation will be analyzed using multivariate linear regression for changes in each of the QST measures against potential confounding factors, and backward stepwise variable selection will then be performed to identify the parsimonious model structures. Spearman rank-order correlation will be used to quantify the association between changes in each of the QST measures and the changes in clinical pain intensity (NRS).

17.2. The PI, RA and research coordinator received the CITI training. Data will be de-identified and a code will be assigned to each participant.

17.3 Data entry will be validated at random.

17.4 Data (questionnaires, sociodemographic and clinical info) will have identifiers removed and banked for a minimum of 3 years per Federal regulations. Deidentified data will be available to research team: PI, co-I ([name] and [name]), RA, statistician ([name], CON). Data will be stored on a password-protected computer. The computer will be stored in a locked room. Any data collected online will be stored on an encrypted data server at the CON. Any downloaded data will be stored on a password protected computer. The RA supervised by the PI will be responsible for data receipt. [name] and [name] will assist with results interpretation.

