Study title:

Feasibility, Acceptability, and Preliminary Efficacy of Combined Transcranial Direct Current Stimulation and Mindfulness for Pain After Total Knee Arthroplasty

NCT Number: NCT05673720

Statistical analysis plan

October 10th, 2025

Data analysis was performed with R (Vienna, Austria) version 4.1+. Baseline demographic information was summarized using descriptive statistics. The distribution of all variables was examined before any analysis, using appropriate statistical tests like Shapiro's test for normality checking. If the assumption of normality was not met, equivalent non-parametric approaches were employed. Comparison between groups on changes from baseline in clinical variables as well as effect size (Cohen's d) calculation were conducted using Wilcoxon rank-sum test for score changes with non-normal distribution, and t -test for score changes with normal distribution. Considering the numerous repeated measures and the possibility of imbalances between measures, we conducted an analysis using a generalized mixed effects model to evaluate changes in all outcome measures for both preoperative and postoperative outcomes. Mixed effects models capture more information by offering more flexibility in the presence of missing data and treat time as a continuous variable. Mixed effects models are used for longitudinal observations and are capable of automatically adjusting for baseline differences, accounting for potential confounders (e.g., anxiety) when needed.

For the preoperative period, the analysis looked at differences between preoperative baseline and after 5 sessions with three fixed effects: Condition (Control vs. Treatment), Time (First vs. Last Session) and their interaction Condition*Time to test whether the treatment group showed different patterns of change compared to the control group over time in the preoperative period. For the postoperative period, the analysis looked at differences 1) between Day 1 Post-op vs. Day 5 Post-op, and 2) between Day 1 Post-op vs. 1-month post-op. Our model included three fixed effects: Condition (Control vs. Treatment), Time (Day 1 vs. Day 5 or Day 1 vs. 1-month post-op), and their interaction (Condition*Time) to test whether the treatment group showed different patterns of change compared to the control group over time in the postoperative period.

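### Early postoperative pain is assessed on different days in the protocol and the SAP, and the SAP's Day 1-referenced interaction does not test Hypothesis 2

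*Protocol*

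**What the plan says.** **Protocol 2.2, Hypothesis 2.** Pain intensity and pain interference are predicted to be lower in the active arm "5 days and 1 month after TKR".

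**Protocol 4.0, text.** "Outcome measures will be taken at 4 time points". The third of these is described only as after surgery, with no day given.

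**Protocol 4.0, schedule table.** The column run reads "Day 5 Day 1 Day 2 Day 3 Month 1". The leading Day 5 is the last preoperative column, so there is no postoperative Day 5 column. NRS, BPI, PHQ-4 and PCS are marked at baseline, preoperative Day 5, postoperative Day 3 and Month 1. Postoperative Day 1 is marked only for analgesic consumption.

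**Protocol 17.1, Aim 2.** The early comparison is of change "from baseline to Day 3 in the postoperative phase", by regression controlling for baseline. The later one involves "comparing the clinical pain intensity changes from baseline to 1 month between the active and the sham groups".

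**Protocol 6.2, Pain severity.** There are four NRS items. Two are present pain, on movement and at rest. Two look back over a week, for example "average pain upon movement in the past 7 days".

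**SAP.** A mixed model is applied to every outcome measure. Its postoperative contrasts are "between Day 1 Post-op vs. Day 5 Post-op" and Day 1 against 1 month, with fixed effects for Condition, Time and Condition*Time. The interaction is the term given for comparing the arms' patterns of change. The SAP also compares the arms on change from baseline by t-test or Wilcoxon test, without naming a postoperative day.

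**The concern.** The early assessment day differs between the hypothesis, the schedule and the SAP, and the reference point moves as well. The protocol measures change from a preoperative baseline taken before any stimulation. The SAP measures change from postoperative Day 1, by which time the intervention is over. The change of reference is the more serious of the two, because it changes the question from whether treated patients have less pain after surgery to whether their pain changes differently once Day 1 has passed.

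Pain intensity and interference are the stated secondary objective. If the interaction is reported as the test of Hypothesis 2, a null result could coexist with a real benefit, and a reader could not tell which prespecified comparison had been carried out.

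**Working it through.** The plan gives no figure to reproduce. The check sets the texts side by side, then looks at what the SAP's term estimates and at the recall windows.

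**1. Postoperative days for the four questionnaires**

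| Source | Early day | Late day | Reference |
|---|---|---|---|
| Protocol 2.2, Hypothesis 2 | Day 5 | 1 month | not stated |
| Protocol 4.0, schedule | Day 3 | Month 1 | preoperative baseline collected |
| Protocol 17.1, Aim 2 | Day 3 | 1 month | preoperative baseline |
| SAP mixed model | Day 5 | 1 month | postoperative Day 1 |
| SAP change-from-baseline comparison | not stated | not stated | baseline |

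The SAP model needs three postoperative occasions: Day 1, Day 5 and 1 month. Only 1 month is scheduled for these questionnaires. The one scheduled early occasion, Day 3, does not appear in the SAP. The Day 3 reading does not depend on how the table was extracted, because the Aim 2 text gives the same day.

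**2. What the interaction estimates**

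Protocol 6.1 places the sessions from T-5 to T-3, where T is the day of surgery, so treatment is complete before postoperative Day 1. Let D(t) be the mean difference in pain, active minus sham, at postoperative time t. With Day 1 as reference:

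- Condition*Time, Day 1 vs Day 5 = D(5) − D(1)
- Condition*Time, Day 1 vs 1 month = D(1 month) − D(1)

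Hypothesis 2 is a statement that D(5) and D(1 month) are below zero. Suppose there is a benefit of size b on Day 1 that stays constant:

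- D(1) = D(5) = D(1 month) = −b
- Interaction at Day 5 = −b − (−b) = 0, and likewise at 1 month

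If the benefit is present on Day 1 and shrinks to c, with 0 < c < b, the interaction is −c + b > 0. That has the sign of harm although the active arm still has less pain. The protocol's contrast from preoperative baseline would have expectation −b in the first case and −c in the second, given comparable arms at baseline.

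**3. Recall windows of the two 7-day NRS items**

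Days of the window before surgery = 7 − postoperative day:

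- Day 3: 7 − 3 = 4 of 7
- Day 5: 7 − 5 = 2 of 7
- Day 1, the SAP's reference: 7 − 1 = 6 of 7

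These are elapsed days. Counting calendar days that include the day of assessment gives the same figures if the day of surgery is put on the preoperative side, and one fewer otherwise. The assessment day therefore alters what the 7-day items measure. It also means the algebra in step 2 applies cleanly to the present-pain items. A 7-day rating on Day 1 is largely a preoperative rating that overlaps the session days.

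**The case against.** Several points can fairly be made for the plan.

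- **Pilot status.** Pain is a secondary endpoint in a pilot of 40 whose primary objective is feasibility and acceptability, and the SAP regards its work as hypothesis-generating. That can excuse loose error control. It does not remove the need to say which day and which contrast represent the hypothesis.
- **Other SAP terms.** The model includes a Condition main effect, which with Day 1 coded as reference estimates the Day 1 difference, and there is a separate change-from-baseline comparison. Either could show a constant benefit. But the SAP assigns the arm comparison over time to the interaction, the fixed effects listed do not include the preoperative value, and the change-from-baseline comparison has no postoperative day attached.
- **Recall items.** Both arms share the preoperative days in the recall window, so the likely effect is dilution rather than bias, and two present-pain items are already in the battery. This stands. The recall point bears on which item should lead and does not invalidate the measure.

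Stronger readings are tempting, and the documents do not support them:

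- A reader might infer three mutually incompatible definitions. There are two early days, 3 and 5, plus a changed reference. Hypothesis 2's days are contained in the SAP's set, and 1 month is common to all the sources that name days.
- A reader might infer that the SAP uses visits absent from the protocol. Postoperative Day 1 is a schedule column, though only for analgesic consumption, and opioid doses are to be recorded for 5 days. The gap concerns the questionnaires.
- A reader might infer that the SAP model could not be fitted. The SAP is dated October 10th, 2025 and reports completed analyses, so an undocumented change of assessment days is more plausible.
- A reader might infer that the day was picked after the results were seen. Nothing dates the change, so this can be neither shown nor excluded.

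**Conclusion.** The conflict is real for NRS, BPI, PHQ-4 and PCS. Of the SAP's three postoperative occasions, two (Day 1 and Day 5) are not scheduled for these measures, and the scheduled Day 3 is unused. The SAP's Day 1-referenced interaction does not test Hypothesis 2: it is zero for any benefit that is established by Day 1 and constant, and reversed in sign for one that then shrinks. The remaining route to the hypothesis, the change-from-baseline comparison, is incomplete without a day.

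The conclusion rests on two readings of the text: that the SAP's model of all outcomes includes pain, and that Day 1 means the first postoperative day, after the sessions that end at T-3. It does not depend on knowing which days were collected, which the documents do not say. The loss cannot be expressed as power, because neither document gives an effect size or standard deviation.

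**What to change.** 1. State in the SAP on which postoperative days the four questionnaires were actually collected, with the number of participants per arm on each day, and when and why collection departed from the scheduled Day 3. Report this as a protocol deviation. Do not rewrite Hypothesis 2 or the schedule to match, since that would hide the departure.
2. Define the Hypothesis 2 test as the between-arm difference at one early day and at 1 month, each adjusted for the preoperative baseline value. This restores the form of the protocol's own Aim 2 analysis. If more than one early day was collected, give a reason for the choice that does not rest on results. If Day 5 is among them, it has the advantage of being the day Hypothesis 2 names.
3. Tie the change-from-baseline comparison to the same two occasions, and label the Day 1-referenced contrasts as exploratory.
4. At the early day, make the two present-pain NRS items the main measures. Report the 7-day items there with a note on the recall window. At 1 month that window is wholly postoperative.

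The cost is a modest re-analysis and a disclosed deviation. The preoperative baseline and the present-pain items are already part of the planned data. Whether any particular early day is complete has to be established from the records.

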3.0 Background*

Osteoarthritis (OA) is a leading cause of disability with 32.5 million adults diagnosed in the United States (US)¹ and the number of people affected is predicted to climb conjointly with life expectancy². TKR is among the three most common inpatient surgeries performed in the US³, and patients undergoing TKR commonly experience acute pain and consume analgesic medications after surgery, more importantly in the first 48-72 hours^{4,5}. While acute pain in the surgical context is expected, greater pain predicts worse outcomes for TKR patients, including chronic post-surgical pain (CPSp)^{4,6} in up to 44% of patients, thus impacting their quality of life⁶⁻⁸. Opioid analgesics have traditionally been used to manage pain related to a TKR procedure^{13,14}. However, the iatrogenic potential of opioids in the perioperative (e.g., respiratory depression, delirium) and postoperative phases (e.g., misuse, addiction, cognitive impairment, decreased level of activity)¹⁵, particularly in older adults, has led to efforts in examining non-pharmacological pain management strategies^{16,17}. Moreover, the current biopsychosocial framework for pain management calls for a multimodal approach¹⁸.

4.0 Study Endpoints*

- 4.1 Measures will be taken by a research assistant via a telephone interview using a Qualtrics® survey. Outcome measures will be taken at 4 time points: 1) baseline (before preoperative active/sham tDCS+MBI), 2) after 5 sessions of preoperative active/sham tDCS+MBI, 3) after surgery, and 4) 1 month after surgery (see table below)
- 4.2 Primary endpoint: Analgesic consumption. The dose of every opioid received within 5 days postoperatively will be transcribed and converted into standardized parenteral morphine equivalents using the Centers for Disease and Control Prevention Guidelines on opioids⁴². A total in milligrams will be calculated for each day and means will be obtained for all groups.
- 4.3 Secondary endpoints: pain severity (numeric rating scale 0-100), pain interference with activities (numeric rating scale 0-10), depression and anxiety (PHQ-4), pain catastrophizing (Pain Catastrophizing Scale), multimodal quantitative sensory testing (QST) including heat pain (e.g., threshold, tolerance), pressure pain threshold, punctate mechanical pain (e.g., suprathreshold ratings and temporal summation), and Conditioned Pain Modulation (CPM), acceptability and feasibility

Day/month	B	Preoperative phase	Postoperative phase
-----------	---	--------------------	---------------------

PROTOCOL TITLE:

		Day 1	Day 2	Day 3	Day 4	Day 5	Day 1	Day 2	Day 3	Month 1
Medical History Questionnaire	X									
Analgesic consumption (primary outcome)							X	X	X	X
Clinical Pain severity (secondary outcome)										
NRS	X					X			X	X
BPI	X					X			X	X
PHQ-4	X					X			X	X
PCS	X					X			X	X
Pain-related Cortical Response (secondary outcome)										
QST measures	X					X				
Acceptability and feasibility										
tDCS + MBI experience questionnaire						X				
Side effects questionnaire		X	X	X	X	X				

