Acceptability and feasibility. We will collect data on participants' tDCS experience via a questionnaire, at the conclusion of tDCS treatment on a 0 (strongly disagree) to 10 (strongly agree) scale: 1) It was easy to prepare the device and accessories; 2) The device was unnecessarily complex; 3) The device was easy to use; 4) I felt the video conferences with a technical person were helpful; 5) I would imagine that most people would learn to use this device quickly; 6) The device was cumbersome to use; 7) I felt confident using the device; 8) I needed to learn a lot of things before I could get going with this device; 9) The effectiveness of the treatment increased over the course of treatment; 10) Overall, I felt that transcranial electrical stimulation treatment benefited me. Moreover, we will evaluate the presence and severity of possible side effects of treatment at the end of each session on a 0 (not at all) to 10 (highest degree) scale. By using open-ended questions, the participants will be asked whether they experienced any side effects, and they will then be asked specifically about tingling, itching sensation, burning sensation, pain at the stimulation site, fatigue, nervousness, headache, difficulty concentrating, mood change, and changes in vision or visual perception. If any side effects are reported, the degree of relatedness to the intervention will be assessed on a 5-point scale. This approach has been used in our previous study and frequently in other studies⁵⁸⁻⁶⁰. Regarding feasibility, we will calculate the percentage of participants who a) met the inclusion criteria, b) agreed to be randomly assigned, c) completed the full tDCS+MBI protocol, and d) attended the follow-up assessment.

6.3 Treatment conditions:

The Food and Drug Administration (FDA) has ruled that the aforementioned tDCS stimulator is a "non-significant risk" device, a requirement for Investigational Device Exceptions. For pain treatment, tDCS is typically delivered

PROTOCOL TITLE:

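### The documents disagree on the primary outcome (feasibility or opioid use) and on the opioid window (5 or 3 days), and the SAP designates no test for Hypothesis 1 on the amount of opioid used

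*Protocol*

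**What the plan says.** **Primary outcome.** In Protocol section 1.0 the primary objective is "Assess feasibility/acceptability of the intervention", and opioid use is not among the objectives there. Section 4.2 names analgesic consumption as the primary endpoint, and the schedule row label begins "Analgesic consumption (primary outcome". The secondary endpoints in 4.3 end with "and Conditioned Pain Modulation (CPM), acceptability and feasibility". The SAP names no primary outcome.

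**Opioid window.** Section 4.2 states: "The dose of every opioid received within 5 days postoperatively will be transcribed and converted into standardized parenteral morphine equivalents". Section 6.2 repeats this and adds: "A total in milligrams will be calculated for each day and means will be obtained for all groups". The schedule marks analgesic consumption on postoperative Days 1, 2 and 3 and at Month 1. It has no postoperative Day 4 or Day 5 column and no baseline mark for this row. The Aim 1 analysis in section 17.1 uses three consecutive days.

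**Test.** Hypothesis 1 (section 2.2) is that "participants receiving preoperative active tDCS+MBI will show reduced postoperative analgesic consumption". For Aim 1, section 17.1 reduces each participant's opioid use to one number, compares the arms by a two-sample t-test or non-parametric alternative, and follows with adjusted regression. The SAP does not mention opioids or analgesics. It describes between-group tests on change from baseline, and a mixed model for every outcome with Condition, Time and Condition*Time. The postoperative contrasts are Day 1 against Day 5 and Day 1 against one month. The stated aim is to see whether the arms change differently over time.

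**The concern.** A reader cannot tell from the documents which result is the headline or how many days of opioid use it covers. Nor can a reader find, in the SAP, the analysis that answers Hypothesis 1.

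The hypothesis is about how much opioid is used. A Condition*Time interaction asks whether the gap between arms changes between two time points. A treatment that lowers use equally on both days leaves that interaction at zero in a linear model. If the active arm uses less on Day 1 and the gap closes by Day 5, the sham arm shows the steeper fall. Read alone, the interaction then favours sham although the active arm used less.

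The SAP is dated October 2025 and written in the past tense. With outcome, window and test all open, a choice among them could appear to have followed the data, whether or not it did.

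**Working it through.** There is no power or sample-size figure in the documents to reproduce: section 12.1 gives 40 completers without an effect size or SD. The main check is a comparison of the texts.

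| Item | Place | What it gives |
|---|---|---|
| Primary outcome | Protocol 1.0 | Feasibility/acceptability |
| | Protocol 4.2, schedule | Analgesic consumption |
| | Protocol 4.3 | Feasibility is secondary |
| | SAP | None named |
| Opioid window | Protocol 4.2, 6.2 | 5 days |
| | Schedule | Days 1-3 and Month 1 |
| | Protocol 17.1, Aim 1 | 3 days |
| | SAP (opioids not named) | Day 1 vs Day 5; Day 1 vs one month |
| Test of amount used | Protocol 17.1, Aim 1 | Between-arm test of one summary |
| | SAP | None designated |

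The SAP's methods, taken in turn for opioid use:

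- *Change from baseline.* This does not fit, because no baseline opioid measure is scheduled.
- *Condition\*Time.* If the model for every outcome is applied to opioid use, this tests change and not amount.
- *Condition.* This term is in the model, but it is not designated for Hypothesis 1 and its coding is not given. If Control and Day 1 are the reference levels, it is the Day 1 difference only. In any case it uses two time points, not the window.

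**Illustration of size.** Assumptions, none in the documents: linear model, n = 20 per arm (40 at 1:1), Day 1 reduction of 0.8 SD, equal between-day correlation ρ of 0.3, 0.5 or 0.7, two-sided 0.05. Power comes from the noncentral t with 38 df and noncentrality (Δ/SD)·√(n/2).

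*Equal daily SD of 1, constant reduction.* The SD of a k-day mean is √((1+(k−1)ρ)/k).
- 3-day, ρ = 0.5: SD = √(2/3) = 0.816; Δ/SD = 0.980; noncentrality 3.10; power 0.855. Over ρ = 0.3/0.5/0.7: 0.922/0.855/0.787.
- 5-day, ρ = 0.5: SD = √(3/5) = 0.775; Δ/SD = 1.033; noncentrality 3.27; power 0.889. Over ρ: 0.960/0.889/0.807.
- Condition*Time: Δ = 0.8 − 0.8 = 0; power 0.05.
- Condition: 0.693 if Day 1 only; 0.864/0.812/0.762 if averaged over Days 1 and 5.

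*SD falling linearly to s by Day 5, reduction proportional to SD.* For Condition*Time, Δ = 0.8(1−s) and SD = √(1+s²−2ρs).
- s = 0.5, ρ = 0.5: Δ = 0.4; SD = √0.75 = 0.866; power 0.296. Over ρ: 0.24 to 0.38.
- s = 0.25, ρ = 0.5: Δ = 0.6; SD = √0.8125 = 0.901; power 0.537. Over ρ: 0.49 to 0.59.

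*Reduction fading linearly to zero (0.8, 0.6, 0.4, 0.2, 0).* The 3-day mean effect is 0.6 and the 5-day mean effect is 0.4.
- Equal SD: 3-day power 0.716/0.620/0.543, 5-day power 0.460/0.357/0.293, a gap of 25 to 26 points. Condition*Time has 0.549/0.693/0.889.
- With SD falling to a half the gap is 13 to 19 points; to a quarter, 5 to 11 points.
- Sign: active change minus sham change = 0.8 − 0 = +0.8, so the active arm falls less although it used less.

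**The case against.** On the primary outcome and the window there is little to say in defence. Separating objective from endpoint does not help, because feasibility is primary in one section and expressly secondary in another. Three days could be a subset of five, but no passage says so.

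On the test, several points for the plan stand:

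- A reader might infer that the SAP offers nothing but a test of change. It does not: Condition is one of three fixed effects. If coded with Day 1 as reference, it would show the Day 1 difference with the right sign. The supportable statement is that no test is designated for Hypothesis 1.
- A reader might infer that Day 5 in the SAP has no source. Hypothesis 2 sets pain outcomes at 5 days and 1 month, so the postoperative model may have been written mainly for pain. Applying it to opioid use is an inference from its coverage of every outcome. Even so, the schedule marks pain on Day 3, and opioid use is the only outcome it marks on postoperative Day 1.
- A reader might infer that the interaction is always near-powerless. That rests on a constant reduction, equal SDs and a linear scale. The SAP says generalized model and states no link; under a log link with falling use, a constant absolute reduction gives a non-zero interaction favouring the active arm.
- A reader might infer from the Background ("consume analgesic medications after surgery, more importantly in the first 48-72 hours") that the treatment effect fades. That sentence concerns when analgesics are used, not how a treatment effect evolves.
- Misreading the interaction's sign would require ignoring Condition and the daily group means promised in 4.2 and 6.2.
- A reader might infer that feasibility will be computed on completers only. Section 6.2 ("Regarding feasibility, we will calculate the percentage of participants who a) met the inclusion criteria") does not do so, and the 40 completers are a recruitment target.

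The SAP also presents the trial as a hypothesis-generating pilot. That weakens any argument from power, but it does not settle which outcome, window and test are meant.

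**Conclusion.** The point holds, and the passages must be reconciled before results are presented as primary. The conflicts on primary outcome and window are plain on the current text. The missing designated test for Hypothesis 1 is also plain; that the interaction would be used for opioid data is probable from the SAP's wording but not stated.

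The size is illustrative and rests on the assumptions shown. With a constant reduction and equal SDs, Condition*Time has 5% power against 79-92% (3-day) or 81-96% (5-day). With SD falling and a proportional reduction it has 24-59%. If the effect fades to zero, the choice of 3 or 5 days moves power by roughly 5 to 26 points, and the interaction's sign runs opposite to amount used. The conclusion does not depend on these figures.

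A reader might go further and infer that Day 4-5 doses were never collected, or that the outcome was changed after seeing results. The documents show neither: they do not say which days were collected, and they give no reason for the differences between protocol and SAP.

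**What to change.** 1. Name one primary outcome, the same in Protocol 1.0, 4.2, 4.3, the schedule and the SAP.
2. Give one opioid window in 4.2, 6.2, the schedule and Aim 1, matching the days actually collected. State whether Days 4 and 5 were collected, and state the role of the Month 1 opioid measurement.
3. In the SAP, restore the protocol's between-arm comparison of the per-participant opioid summary over that window (t-test or Wilcoxon, with a 95% CI) as the test of Hypothesis 1.
4. Label Condition*Time for opioid use as supportive and report it beside the arm means for each day.
5. Disclose, date and explain any departure from the protocol's primary endpoint, window and test.

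The cost is wording in both documents, one simple analysis and a disclosure statement. If Days 4 and 5 were not collected, the endpoint becomes a narrower 3-day one, and any re-ranking of the primary outcome has to be reported as a late change.
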